13.7.3 Subgroup Analyses

The primary efficacy endpoint and the secondary efficacy endpoint visualization in mangoral-enhanced MRI vs. unenhanced MRI will be also evaluated in the following subgroups of patients:

- Subgroups of patients by the MRI scanner's magnetic field strength 1.5 Tesla and 3 Tesla.
- Subgroups of patients by the lesion type (benign, malignant, unknown, malignant: HCC, malignant: metastasis)
- Subgroups of patients with age < 65 years and ≥ 65 years.

- Subgroups of patients by eGFR: < 15, \geq 15 to \leq 30 and $>$ 30 mL/min/1.73 m 2 .
- Subgroups of patients by sex

These subgroup analyses will be done using the FAS population. Additional subgroup analysis may be done by race and/or ethnicity depending on the availability of data. A forest plot will be produced to show the comparison of paired differences (mean difference and 95% confidence interval) for the primary analysis and subgroup analysis in both BD and LC for combined vs. unenhanced and enhanced vs. unenhanced.

For lesions diameter (small lesion (diameter $<$ 1 cm); medium lesion (diameter \geq 1 to \leq 3 cm); large lesion (diameter $>$ 3 cm)), subgroup analyses will not be done for the primary endpoint but for the below outputs on FAS:

- Number of lesions detected by MRI method: This will summarize number of lesions by lesion diameter category and methods.
- Number of patients with at least one new lesion identified compared to unenhanced MRI: This will summarize for patients with new lesions if they are categorized as small, medium or large. The denominator for percentages will be number of patients in the FAS.

13.7.4 Pharmacokinetic Analysis

The analysis of PK parameters will be performed using the PK Set (PKS). Descriptive and graphical methods will be used to summarize the study results.

The CV and the geometric mean will be additionally included in the descriptive analyses of PK parameters, except for t_{max} . The 2-sided 95% confidence intervals for the geometric means of C_{max} , AUC_{0-t} and AUC will be constructed.

Missing data will be treated as such and will not be imputed or replaced in any way if not specified otherwise.

Individual, mean and overlay blood concentration-time profiles will be plotted on both linear and semi-logarithmic scales. Individual values and descriptive statistics for blood concentration data will be presented by the nominal time point using the Safety Population.

13.8 Safety Analysis

The analysis of safety data will be performed using the SAF. Safety data will be summarized using descriptive statistics.

13.8.1 Adverse Events

Safety analysis will include the investigation of adverse events (AEs), serious adverse events (SAEs), AEs related to IMP and SAEs related to IMP.

The following events shall be reported always as SAEs:

- seizure
- stroke
- cerebral venous thrombosis
- QTcF or QTcB greater than 480 msec
- OTcF or QTcB increase of 60 msec over baseline

For all AEs, a summary containing the following counts of patients, percentages of patients and number of events will be presented by pre and post dose (per CRF):

- Number of AEs;
- Number of related AEs;
- Number of AEs leading to study discontinuation (AE caused the patient to be discontinued from the study);
- Number of related AEs leading to study discontinuation;
- Number of SAEs;
- Number of related SAEs;
- Number of grade 3 or greater AEs;
- Number of grade 3 or greater related AEs;
- Number of AEs recovered;
- Number of AEs recovering;
- Number of AEs with outcome of death.

Further, all AEs, SAEs, AEs related to IMP and non-serious AEs will be summarized in a frequency table by MedDRA system organ class (SOC) and preferred term (PT), presented by pre and post dose (per CRF). The version of the utilized dictionary will be presented as part of the provided tables and listings. Tables will be sorted by decreasing frequency for SOC then PT within SOC using the overall column.

A summary of AEs by SOC, PT and maximum CTCAE grade will be presented.

Additionally, a summary of frequent post dose AEs (experienced by $\geq 5\%$ of dosed patients) by PT will be displayed summarizing time to event (hours) and duration of event (hours) with summary statistics. For handling partial date/times refer to [Section 15.1.4.1](#). If an AE has no end date (ongoing at end of study) this will not be included in the analysis of duration of event.

All AEs, SAEs (other than death) and AEs leading to study discontinuation will be listed. In addition, a listing for AEs leading to death will be presented. Listings of AEs leading to death and SAEs (other than death) will be presented on screened patients and other AE listings will be presented on enrolled patients.

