#### **6.3.7.2      Assessment of adverse events**

The investigator will identify the occurrence of pre-dose events and / or AEs through non-leading questioning and examination of the patient.

For each AE, the investigator will document the following:

- **Signs and symptoms** of the event (if a specific disease can be diagnosed, this disease should be the reported AE; if only signs and symptoms can be evaluated, each sign or symptom should be reported as a separate AE)
- **Onset date and time** (if a change from pre-dose in a laboratory test is reported as an AE, the start date is the date of collection of the first laboratory sample that shows the change)
- **End date and time** (if a change from pre-dose in a laboratory test is reported as an AE, the end date is the date of collection of the first laboratory sample that shows a return to pre-dose level)
- **Measure taken** (none, drug treatment required, hospitalisation or prolonged hospitalisation, study discontinuation, other measures [specification])
- **Outcome** (recovered/resolved, recovering/resolving, recovered/resolved with sequelae, not recovered/not resolved, fatal, unknown)

In addition, each AE will be rated by the investigator according to the following categories (the sponsor must carry out a separate assessment for causal relationship, seriousness, and expectedness):

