#### **6.3.7.3 Follow-up of adverse events**

Each unresolved AE at the patients' individual study termination must be followed up until it subsides or until the cause is known or an adequate final assessment can be given. The maximum follow-up period will be 4 weeks after the patient's study termination. If after 4 weeks no final outcome can be acquired, the outcome of the AE is 'unresolved'.

For all patients with clinically significant abnormal laboratory findings at 5 ( $\pm$  2) days post-dose compared to the baseline evaluation (within 24 hours prior to the administration of IMP), the laboratory test will be repeated to ensure the validity of the abnormal result. Confirmed abnormal values will be followed up until normalisation to baseline level or until there is no medical necessity for further blood tests in the investigator's opinion. Therefore, the patient might have to come to the site for one or more unscheduled follow-up visits.

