15.1.4 Safety analysis

15.1.4.1 Adverse events

The result of all imputation strategies (e.g., incomplete start dates of adverse events) and new derived information must be stored in the corresponding analysis dataset.

Handling of missing date information

The term missing date/time refers to a completely missing date/time or to an incomplete date/time where parts are not available, e.g., missing hours.

Missing start and end date/times will be imputed conservatively, i.e., missing values will be imputed in such a way that the duration of the adverse event is considered with the longest possible duration.

Imputation

I1: Impute AE start date with:

A replacement of missing year for AE start information is not foreseen. If needed, this will be considered on a case-by-case decision which must be documented.

a) If year of AE is the same as year of treatment then set start date to the date of treatment, otherwise use first calendar day and/or first calendar month.

Imputation will be done based on the available partial information starting with month and then day:

Missing date	Date of treatment	Imputed date
2014-Mar	2014-Mar-XX	2014-Mar-XX
2014-Mar	Not 2014-Mar	2014-Mar-01
2014	2014-XXX-XX	2014-XXX-XX
2014	Not 2014	2014-Jan-01

b) First hour and/or first minute.

Imputation will be done based on the available partial information starting with hour and then minutes:

Missing time	Date time of treatment	Imputed time
11:--	11:XX	11:XX
11:--	Not 11	11:00
--:--	Known	Time of treatment
--:--	Unknown	00:00

I2: Impute AE stop date with:

a) Last calendar day and/or calendar last month.

Imputation will be done based on the available partial information starting with month and then day. The respective last month and day will be chosen for imputation:

Missing date	Imputed data
2014-Mar	2014-Mar-31
2014	2014-Dec-31

For February, leap years must to be taken into account when calculating the last day in February.

b) Last hour and/or last minute.

Imputation will be done based on the available partial information starting with hour and then minutes. The respective last hour of a day and last minute will be chosen for imputation. "23:59" will be considered as the last hour/last minute per day.

Missing time	Imputed time
11:--	11:59
--:--	23:59

List of deaths

Death will be identified by the outcome of adverse event if the outcome equals "fatal" or reason for end of study is "dead".

Patient experiencing a non-serious adverse event

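### The AE duration summary leaves out ongoing events and so can only err downward for any frequent AE still open; imputed stop dates have no cap, and three of six collected outcomes have no row

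*SAP*

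**What the plan says.** SAP 13.8.1 plans one table of time to onset and duration, in hours, for post-dose AEs that reach the 5% frequency threshold. Its rule for open events is: "If an AE has no end date (ongoing at end of study) this will not be included in the analysis of duration of event".

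Other parts of the plan bear on this:

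- SAP 11.1.2 counts an AE with an unknown end date as ongoing. SAP 11.2.1 (Table 7) gives an AE marked ongoing, or lacking an end date, the duration category 'ongoing'. Section 13.8.1 names no table that shows this category.
- SAP 15.1.4.1 sets the general principle that "missing values will be imputed in such a way that the duration of the adverse event is considered with the longest possible duration". Its stop-date rule moves a year-month date to the last day of that month and a year-only date to 31 December. It sets no upper limit.
- The AE overview in SAP 13.8.1 has three outcome rows: "Number of AEs recovered", "Number of AEs recovering" and "Number of AEs with outcome of death".
- Protocol 6.3.7.2 has the investigator record six outcomes. After recovered and recovering, the list continues "recovered/resolved with sequelae, not recovered/not resolved, fatal, unknown".
- Protocol 6.3.7.3 limits the pursuit of unresolved AEs: "The maximum follow-up period will be 4 weeks after the patient's study termination". An AE without a final outcome by then is recorded as unresolved.

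**The concern.** Whether an event enters the duration summary depends on the quantity being summarised. A long event is more likely to be open at last contact, and an open event is left out. The remaining mean and median describe only the events short enough to have ended in time. A reader of the table cannot tell how many were left out, because no count of ongoing events is planned beside it.

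The imputation rule can push the other way. A partial stop date may be moved beyond the last AE contact, or beyond death, and the resulting duration enters the same table as if it had been observed. The table could therefore omit real long events and include artificial ones.

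The overview does not fill the gap. Recovery with sequelae, non-recovery and unknown outcome have no row of their own, although they are the non-fatal outcomes a safety reader would most want to see separately.

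**Working it through.** **Outcomes collected against outcomes tabulated**

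| Protocol 6.3.7.2 | Row in SAP 13.8.1 |
|---|---|
| Recovered | yes |
| Recovering | yes |
| Recovered with sequelae | none named |
| Not recovered | none named |
| Fatal | yes |
| Unknown | none named |

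That is 6 collected, 3 tabulated and 3 without a row. For event counts, total − recovered − recovering − death returns the three missing outcomes as one pooled number. For patient counts the subtraction fails, because one patient may have events with different outcomes. The SAP does not say whether its recovered row includes recovery with sequelae.

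**Direction and possible size of the duration bias**

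The plan states no AE duration and no proportion ongoing, so there is no figure to reproduce. The inputs are:

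- Threshold: 5% of 80 patients (SAP 9.3) = 4 patients.
- Longest duration that can be observed, C. Protocol 7.4.1 puts the core phase at 4–5 days, so C = 5 × 24 = 120 h if end dates stop at the day-5 visit. If they are captured through the further 4 weeks, C = (5 + 28) × 24 = 792 h, which is day 33. The documents do not settle which applies to the table. Both values assume onset near dosing.
- Assumption, not from the documents: durations D are exponential with mean m, and censoring is independent of D.

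The formulas are:

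- Share left out = exp(−C/m).
- Resolved-only mean = m − C·exp(−C/m) / (1 − exp(−C/m)).
- True median = m·ln 2. Resolved-only median = −m·ln(1 − p/2), with p = 1 − exp(−C/m).

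Worked case, m = 240 h and C = 120 h: exp(−0.5) = 0.607, and 240 − 120 × 0.607/0.393 ≈ 55 h, so the ratio is 55.0/240 = 0.23.

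| C (h) | True mean m (h) | Left out | Resolved-only mean (h) | Ratio to m | True median (h) | Resolved-only median (h) |
|---|---|---|---|---|---|---|
| 120 | 24 | 0.7% | 23.2 | 0.97 | 16.6 | 16.5 |
| 120 | 72 | 18.9% | 44.1 | 0.61 | 49.9 | 37.5 |
| 120 | 120 | 36.8% | 50.2 | 0.42 | 83.2 | 45.6 |
| 120 | 240 | 60.7% | 55.0 | 0.23 | 166.4 | 52.6 |
| 792 | 120 | 0.1% | 118.9 | 0.99 | 83.2 | 83.0 |
| 792 | 240 | 3.7% | 209.7 | 0.87 | 166.4 | 157.7 |
| 792 | 672 | 30.8% | 320.0 | 0.48 | 465.8 | 285.5 |

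The direction does not depend on the exponential form: under independent censoring, the mean of D given D ≤ C cannot exceed the mean of D.

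**Invented small example.** Ten events of one term: eight end after 6, 8, 12, 12, 24, 24, 36 and 48 h, and two are ongoing at 792 h. Resolved only: mean 170/8 = 21.25 h, median (12 + 24)/2 = 18 h. Treating the two as censored, the Kaplan–Meier curve is at 6/10 after 12 h and 4/10 after 24 h, so the median is 24 h with two ongoing.

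**Uncapped imputation (assumed dates).** For an AE starting on 1 March with a stop date known only to the year, the rule gives 31 December: about 305 × 24 = 7,320 h, against a follow-up ceiling of about 792 h. With the month known as March, it gives 31 March: about 30 × 24 = 720 h.

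**The case against.** The strongest reply is that the rule touches one descriptive table in a single-arm safety analysis. Ongoing AEs still count in the total, related, serious and grade 3 or higher rows and in the SOC/PT and maximum-grade tables, and every AE is listed. That is correct and limits the point.

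The bias may also be negligible. Protocol 1.1.4 describes reactions as mainly mild, transient gastrointestinal symptoms, and for short events almost nothing is left out. Year-only stop dates should be rare, since Protocol 6.3.7.2 asks for end date and time and Protocol 9.1 provides for data queries. Both arguments stand as to size, but neither justifies the rule. The output shells are a separate document (SAP 7.0), so an ongoing count may appear there; what can be said is that 13.8.1 names none.

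Three stronger readings are tempting, and the documents do not support them:

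- *The rule hides neurotoxicity.* The table covers only terms reaching 5%, about 4 of 80 patients. A rare neurological event would be absent however ongoing AEs were handled. Neurological assessments are separately summarised and listed (SAP 13.8.3).
- *The overview inflates recoveries.* Omitting a row for non-recovery adds nothing to the recovered count. The loss is one of detail.
- *The exclusion flatly contradicts the longest-duration principle.* The general sentence in 15.1.4.1 does define missing dates to include completely missing ones, but the operative stop-date rule works from partial information. Sections 11.1.2, 11.2.1 and 13.8.1 agree with each other on AEs without any end date.

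Finally, having no end date is not the same as never resolving. Some of these events may end after last contact, and some end dates may simply not have been recorded.

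**Conclusion.** The point holds as a limited defect in safety presentation. If any frequent post-dose AE is ongoing, the planned duration summary is biased downward under independent censoring, and no output named in 13.8.1 shows how many events were left out. The uncapped imputation is a separate fault that can overstate duration. The two need not cancel, because imputing a partial date does not bring back an event with no end date.

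The actual size is unknown. It is zero if no frequent AE is ongoing, and small if events are short or end dates are captured through the 4-week follow-up. The ratios from 0.97 down to 0.23 (120 h) and from 0.99 down to 0.48 (792 h) rest on assumed exponential durations and assumed means, so they show a range and do not predict this trial's result. The missing outcome rows follow directly from comparing the two documents. The primary efficacy analysis and the collection of safety data are unaffected.

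**What to change.** Amend the SAP before database lock:

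1. In 13.8.1, show the number of ongoing events beside each duration summary, using the category already defined in 11.2.1.
2. Report a median duration that treats ongoing AEs as censored at the last AE contact, by Kaplan–Meier where numbers allow. If the curve does not reach one half, report the median as not reached. State whether end dates obtained in the 4-week follow-up are used.
3. In 15.1.4.1, cap every imputed stop date at the earlier of last AE contact and death.
4. Tabulate all six collected outcomes in the overview, and state how the unresolved outcome of Protocol 6.3.7.3 maps to them.

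No new data are needed. The cost is SAP wording and minor programming. The drawback is that censored medians will be unstable for terms with few events, possibly only about four patients, and a patient may contribute more than one event. For such terms the ongoing count with the listing may be all that is worth reporting.

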13.8.2 Vital Signs

Summary statistics for vital signs specified in [Section 9.2.4.1](#) and their changes from baseline will be presented.

All vital signs data will be listed.

13.8.3 Physical Examination and Neurological Assessments

Parameters of physical examination (specified in [Section 9.2.4.2](#)) and neurological assessments (specified in [Section 9.2.4.3](#)) there will be summarized using descriptive statistics.

All physical and neurological examination data will be listed.

13.8.4 12-Lead ECG

Summary statistics for 12-lead ECG parameters specified in [Section 9.2.4.4](#) and their changes from baseline will be presented.

Additionally, the number and percentage of patients with maximum QT value in certain ranges per ICH E14 will be summarized (≤ 450 msec, 450 to 480 msec, 480 to 500 msec and > 500 msec). The number and percentage of patients with maximum change from baseline in QT value in certain ranges will be summarized (≤ 30 msec, 30 to 60 msec and >60 msec). All ECG data will be listed.

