### **Seriousness**

A serious adverse event (SAE) is an AE that at any dose:

- Results in death
- Is life-threatening (i.e. the patient was at risk of death at the time of the event; it does not refer to an event that hypothetically might have caused death if it were more severe)
- Requires in-patient hospitalisation or prolongation of existing hospitalisation
- Results in persistent or significant disability/incapacity (defined as a permanent or substantial disruption of the patient's ability to carry out normal life activities)
- Is a congenital anomaly or birth defect

or

- Is an important medical event that does not have to be immediately life-threatening or result in death or hospitalisation, but may, based upon appropriate medical judgment, jeopardise

the patient or may require medical or surgical intervention to prevent any of the outcomes listed above. Examples of such events include allergic bronchospasm requiring intensive treatment in an emergency room or at home, and blood dyscrasias or convulsions that do not result in hospitalisation, or development of drug dependency or drug abuse. Note: events of seizure, stroke, cerebral venous thrombosis, QTcF or QTcB greater than 480 msec or QTcF or QTcF increase of 60 msec over baseline must be reported as serious.

All AEs that do not fall into any of the above categories are defined as non-serious.

Note: planned hospitalisation or prolongation of hospitalisation for a pre-existing condition or a procedure required by this study protocol, without a serious deterioration in health, is not considered an SAE.

**Expectedness** (only evaluated by the sponsor):

Expected: An ADR is considered expected if its description agrees in nature, severity, frequency and specificity with the description of the up-to-date reference safety information included in the investigator's brochure

Unexpected: An unexpected ADR is an adverse reaction for which the nature or severity is not consistent with the applicable product information (e.g., investigator's brochure)

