7.1 Changes from Protocol

The planned analysis will be performed according to the study protocol, its amendments and this statistical analysis plan. If there are contradictions between the study protocol or its amendments and this statistical analysis plan, the analysis will be performed according to this analysis plan. Any deviation from the planned analysis according to the study protocol has to be described in the integrated report.

The protocol states that the per protocol set is all patients in the full analysis set without any important protocol deviations. The SAP has been revised to state that only a subset of important deviations will result in patients being excluded from the per protocol set. All important protocol deviations will be manually reviewed by ICON and Ascelia to agree which could have impact on the per protocol set.

The protocol mentions the requirement for adverse drug reactions (defined per protocol as a causal relationship between a medicinal product and an AE to be at least a reasonable possibility) to be collected

and summarized. However, in this study adverse events are only assessed as related or not related so this will be used for the outputs.

The wording and definition of the PK dialysis subgroup population is amended.

The protocol Section 8.1.5 mentions subgroup analysis to be performed on the co-primary variables to be done by status of liver disease, on the subgroup of patients with PK data and also subgroup of patients with brain MRI, this is not included in the SAP as the patient groups are considered to be too small for a meaningful comparison. Subgroup analysis on the co-primary variables by sex will be added. Additionally subgroup analyses is mentioned in the protocol for by lesion diameter on the primary endpoint, this is not planned but different subgroup analyses is planned as described in [Section 13.6.3](#).

The derivations for liver-to-lesion contrast and contrast to noise ratio are amended slightly as described in [Section 11.2.5](#).

QTcB interval (msec) and QTcF interval (msec) were derived in the database but issues were found with these calculations, for this reason these parameters were re-derived in the datasets per the derivations in [Section 11.2.1](#).

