9.2.4.4 Electrocardiogram (ECG)

A 12-lead ECG will be performed after 5 minutes supine rest at baseline (within 3 hours prior to contrast administration) and after administration of mangoral at 6 (± 1) and 24 (± 4) hours post-dose.

ECG parameters will be recorded and assessed: overall interpretation, heart rate (beats/min), QT interval (msec), RR interval (msec), PR interval (msec), QRS duration (msec), QTcB interval (msec) and QTcF interval (msec).

The investigator will record on the eCRF whether the results are normal, abnormal (not clinically significant or clinically significant). If recorded as abnormal and clinically significant, the abnormality must be specified in the eCRF and if observed after administration of mangoral, the abnormality must also be recorded as an AE.

Note: As specified in Section 6.3.7 of the protocol, if electrocardiographic abnormalities observed in a pre-existing condition are preserved also after the administration of mangoral, these should not be considered as AEs. Only if abnormalities are worsening of pre-existing ones, they are considered as AEs.

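### SAP 13.8.4 specifies both categorical ECG tables on QT rather than QTcF/QTcB, so their outlier counts would not match the plan's own always-serious ECG criteria

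*SAP*

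**What the plan says.** SAP 13.8.4 first promises summary statistics and changes from baseline for the ECG parameters listed in SAP 9.2.4.4. It then adds two categorical tables.

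- **Maximum value:** "the number and percentage of patients with maximum QT value in certain ranges per ICH E14 will be summarized". With a less-than-or-equal sign before the first figure, the bands are "450 msec, 450 to 480 msec, 480 to 500 msec and > 500 msec".
- **Maximum change:** "maximum change from baseline in QT value in certain ranges will be summarized", in bands of 30 msec or less, 30 to 60 msec, and more than 60 msec.

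Neither sentence names a corrected interval. SAP 9.2.4.4 lists QT, QTcB and QTcF as separate parameters, and SAP 11.2.1 gives a formula for each correction. SAP 7.1 explains that the database versions of QTcB and QTcF had calculation problems and that "for this reason these parameters were re-derived in the datasets".

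The events that must always be reported as serious are defined on the corrected intervals. SAP 13.8.1 lists "QTcF or QTcB greater than 480 msec" and "OTcF or QTcB increase of 60 msec over baseline" (the first letter of the second quote is evidently a typing slip for Q). Protocol 6.3.7.2, under Seriousness, has the same rule: "QTcF or QTcB greater than 480 msec or QTcF or QTcF increase of 60 msec over baseline must be reported as serious". It prints QTcF twice in the change criterion, where the SAP names QTcF and QTcB. Protocol 6.3.4 also names the corrected QT interval among the ECG parameters to be assessed.

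**The concern.** The 480 and 60 msec cut-points in the two tables are the same figures as the always-serious criteria, but the criteria are on QTcF/QTcB and the tables are on QT. Uncorrected QT changes with heart rate, so a cut-off on QT selects different patients from the same cut-off on QTc.

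A reader of the study report would naturally take these tables as the count of patients beyond the thresholds and compare them with the SAEs. If they are programmed literally, the two sets of numbers need not agree, and the difference would come from the choice of variable rather than from the drug or from reporting. The protocol itself raises cardiac effects of manganese, in its risk-benefit assessment and in its account of an earlier intravenous manganese agent, so a correct outlier count is worth having.

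**Working it through.** The plan has no figure of its own to reproduce here, because the question is which variable is tabulated. The check classifies the same ECG twice, once on QT as SAP 13.8.4 is written and once on QTc.

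**Inputs**
- Formulas (SAP 11.2.1): QTcB = QT / RR^(1/2) and QTcF = QT / RR^(1/3), with RR in seconds. RR = 60 / heart rate.
- Bands: SAP 13.8.4. Criteria: SAP 13.8.1 and Protocol 6.3.7.2.
- Heart rates and QT values: assumed, because the documents give no distribution. Heart rates from 45 to 100 beats/min are shown.

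**Maximum value, one case in full.** At 90 beats/min, RR = 60/90 = 0.667 s. With QT 430, QTcF = 430 / 0.667^(1/3) = 492 and QTcB = 430 / 0.667^(1/2) = 527. The other rows follow in the same way.

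| QT (msec) | Heart rate (/min) | Row on QT | QTcF | QTcB |
|---|---|---|---|---|
| 430 | 90 | 450 or less | 492 | 527 |
| 440 | 80 | 450 or less | 484.3 | 508.1 |
| 400 | 90 | 450 or less | 457.9 | 489.9 |
| 485 | 50 | 480 to 500 | 456 | 443 |
| 485 | 45 | 480 to 500 | 440.7 | 420.0 |
| 510 | 45 | above 500 | 463.4 | 441.7 |

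The first three ECGs sit in the lowest row of the table yet exceed 480 msec on at least one corrected interval. The last three sit at or above the 480 row without exceeding 480 on either.

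**How unusual the heart rate must be.** Take a QT of exactly 450, the top of the lowest row. QTcB exceeds 480 when the heart rate is above 60 × (480/450)² = 68.3/min. QTcF exceeds 480 above 60 × (480/450)³ = 72.8/min. Ordinary rates are enough. In the other direction, at 50/min a QT of up to 450 × 1.2^(1/2) = 493.0 still has QTcB no higher than 450, and a QT of up to 450 × 1.2^(1/3) = 478.2 still has QTcF no higher than 450.

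**Maximum change**

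| Baseline | Post-dose | Change in QT | Change in QTcF | Change in QTcB |
|---|---|---|---|---|
| 400 at 60/min | 400 at 100/min | 0 (row 30 or less) | +74.3 | +116.4 |
| 380 at 75/min | 445 at 55/min | +65 (row above 60) | +22.9 | +1.2 |

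The first patient meets the 60 msec criterion on both corrections and is tabulated in the lowest row. The second is tabulated in the highest row and is below 30 msec on both.

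**Band limits.** As printed, 450, 480 and 30 each belong to two rows. An increase of exactly 60 msec falls in the 30 to 60 row, while the always-serious criterion is worded as an increase of 60.

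**The case against.** The strongest reply is that the wording is loose shorthand for QTc. SAP 13.8.4 says QT value, not QT interval, which is the SAP's label for the uncorrected parameter. It ties the value ranges to ICH E14, its cut-points coincide with the QTc criteria, and only the corrected intervals are re-derived for analysis. SAP 7.0 places output specifications in separate table shells, and the change log says version 4.0 was aligned with those shells. They are not among the documents, so what would actually be programmed is unknown. This stands as a reason for caution about intent. It does not repair the SAP text, which elsewhere keeps the three intervals apart and nowhere says that QT here means QTc.

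The second reply is that other outputs carry the information, and this largely stands. QTcB and QTcF each receive summary statistics and changes from baseline, and SAP 10.0 includes the maximum among these, so the highest scheduled QTc would be printed. All ECG data are listed. Qualifying events are to be reported, tabulated and listed as SAEs, although the documents do not say whether sites relied on the database QTc values that later proved faulty. None of these outputs, however, is a count of patients by QTc category.

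A reader might go further and infer that true prolongation would be hidden from the report, or that affected patients would be declared normal. The documents do not support either. The outputs above remain, and the lowest row carries only a numerical label. Nor does the SAP call these its principal repolarisation analysis; it introduces the value table as an addition to the parameter summaries. The example of QT 485 at 50/min should also not be oversold: on QTcF it moves down one row, to 450 to 480, and only on QTcB does it reach the lowest row.

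**Conclusion.** Wrong as written. Followed literally, both categorical tables classify patients on a variable other than the one used for the plan's always-serious ECG criteria, and they err in both directions at ordinary heart rates.

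The consequence is confined to the categorical counts. These need not agree with the criteria or with the SAE tables, while the continuous QTc results and listings are unaffected. The misclassification follows from the SAP's own formulas. The particular heart rates and QT values are assumptions, and the number of patients affected in this trial cannot be estimated from the documents. The conclusion also assumes that the unseen shells do not already specify QTcF and QTcB. If they do, the SAP text still needs to say so. No view is taken here on which thresholds are clinically right.

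**What to change.** In SAP 13.8.4:

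1. In both categorical tables, replace QT value with QTcF and QTcB value (re-derived per Section 11.2.1), tabulated separately, taking each patient's maximum on each corrected interval in its own right.
2. Print non-overlapping bands: 450 or less, above 450 to 480, above 480 to 500, and above 500 msec; and 30 or less, above 30 to 60, and above 60 msec. State how an increase of exactly 60 msec is to be counted against the always-serious criterion.
3. Keep uncorrected QT in the descriptive summary only.
4. Confirm that the table shells match. While the text is open, reconcile the wording of the change criterion between Protocol 6.3.7.2 and SAP 13.8.1.

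The cost is a wording edit and a change to the shells for these tables. QTcF and QTcB are already re-derived in the datasets, so no new data are needed.
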